The principles guiding the selection of the following inclusion and exclusion criteria are to ensure the enrollment of participants who meet 3 major criteria: 1) high risk for developing diabetes, 2) no medical contraindications to participate in a lifestyle intervention including unsupervised physical activity and weight loss, and 3) ethical randomization, i.e., there are no compelling reasons that potential participants should be referred for immediate weight loss. Subjects will include 225 overweight or obese adults with pre-diabetes in Forsyth County, NC and the surrounding area. All participants will be required to identify themselves as Hispanic or Latino and we hope to recruit approximately equal numbers of men and women based on their representation in the population of the area. As women are more likely to seek medical care than men, we anticipate at least 50% of our sample to be female. We plan to make concerted efforts to ensure that no less than 40% of our sample is male.

a. Inclusion Criteria

- Demographics: Men and women 18 years of age and older who reside in or near Forsyth County, NC.
- Ethnicity: self-identified as Hispanic or Latino
- Evidence of pre-diabetes: HbA1c of 5.7-6.5%
- Body Mass Index (BMI): 25-45 kg/m²
- Willingness to Accept Randomization: Potential participants must be willing to accept randomization to either the intensive lifestyle intervention or the comparison usual care condition.

b. Exclusion Criteria

- Weight Loss: Currently involved in a supervised program for weight loss.
- Diabetes: Clinical history of diabetes mellitus, or newly diagnosed diabetes mellitus at screening.
- Recent History of Cardiovascular Disease: Clinical history of cardiovascular disease (CVD) occurring within the past 6 months, including myocardial infarction, angina, coronary revascularization, stroke, TIA, carotid revascularization, peripheral arterial disease, congestive heart failure. All persons with recent CVD should be participating in cardiac rehabilitation (with appropriate supervision as indicated) to reduce their risk of recurrence; hence, randomization might raise ethical concerns.

[figure not shown]
- Hypertension: Uncontrolled high blood pressure: BP \geq 160/100. Potential participants can be re-screened after control has been achieved.
- Pregnancy: Pregnancy, breast feeding, or planning pregnancy within 2 years.

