- Other Chronic Conditions: Other chronic disease likely to limit lifespan to less than 2-3 years, including any cancer requiring treatment in past 5 years except non-melanoma skin cancer.
- Medication: Chronic use of medicine known to significantly affect glucose metabolism (e.g., corticosteroids, protease inhibitors).
- Other: Conditions/criteria likely to interfere with participation and acceptance of randomized assignment, including the following: inability/unwillingness to give informed consent, another household member already randomized to La Comunidad, major psychiatric or cognitive problems (schizophrenia, dementia, self-reported active illegal substance or alcohol abuse), participation in another research study that would interfere with La Comunidad.

E. Screening and Randomization

a. Tiered Screening Process

A tiered screening process will be implemented to maximize the efficiency of screening. Interested prospective participants will be identified at the churches, community events, or by advertising, and will complete or be administered an initial pre-screening tool to assess medical history and the diabetes risk screening tool developed by the American Diabetes Association²². If potentially eligible, they will then be invited to take part in an interactive question and answer session to learn more about the study, followed by the informed consent process. Those participants still interested and eligible will then have their height, weight, and blood pressure measured and will complete the physical activity readiness questionnaire (PAR-Q). Those participants who have met all other eligibility criteria will then have a blood draw to determine HbA1c. Figure 2 outlines the screening process that we plan to implement.

Figure 2. Tiered Screening Process for La Comunidad

b. Randomization

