We plan to collect all screening data for this study in community locations (churches, recreation centers, etc). Those participants that meet all eligibility criteria and provide informed consent will complete baseline and follow-up visits at the CRU or Lexington Medical Center. To enable assessment of the process of implementation, impact and outcomes of the intervention, data will be collected at both the individual and program levels. At the individual level, we will collect information regarding demographics, anthropometry (height, weight, and waist), blood pressure, pulse, medical history, health behaviors (diet, physical activity), health-related quality of life (HRQL), healthcare resource utilization and cost. We will also obtain blood samples to measure HbA1c, glucose, insulin, and lipids and to store for future uses. At the program level, we will collect data related to implementation and cost. A schedule of data collection visits for participants is outlined in Table 3. Participants will be followed from the baseline/randomization visit through 24 months or June 30, 2017 (for those participants randomized after July 2015). Anticipated participation in the study will be at least one year for all randomized participants. Study questionnaires will be included in Appendix B as developed/purchased and approved by the Steering Committee.

Table 3. Planned Data Collection for La Comunidad

Measure	Baseline	F06	F12	F18	F24
HbA1c	x	x	x	x	x
Glucose	x	x	x	x	x
Insulin	x	x	x		x
Lipids	x		x		x
Height, Weight	x	x	x	x	x
Blood Pressure	x	x	x	x	x
Waist Circumference	x	x	x		x
Adverse Events		x	x	x	x
Contact Information	x	x	x	x	x
Demographics	x	x	x	x	x
Medical History	x	x	x	x	x
Medication Review	x	x	x	x	x
IPAQ	x	x	x		x
Food Frequency Questionnaire		x	x		x
Short Form 36	x	x	x		x
Behavioral Constructs	x	x	x	x	x
Health Utilities Index	x	x	x		x
Economic Evaluation		x	x	x	x
Stored Blood Samples	x	x	x		x

a. Demographics and Anthropometry

Age (date of birth), gender, race and ethnicity (US Census Definition), and names and contact information for at least 2 informants will be collected. Weight (nearest 0.1 kg), height (nearest 0.5 cm), minimum waist (nearest 0.5 cm) will be measured using standardized methodology as used in HELP PD.

b. Blood Pressure

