program will be minimized by focusing on moderate, as opposed to vigorous, activity and by stressing a start slow and increase slowly approach. We will be encouraging participants to adopt brisk walking as the foundation of their activity program and we will educate participants about the potential risks of increased activity. Potential participants will also be screened using the Physical Activity Readiness Questionnaire. Persons who screen positive will be required to obtain medical clearance from a primary care provider prior to participation. All potential participants will be encouraged to discuss participation with their usual physician prior to enrolling in La Comunidad. An informational brochure will be developed so that potential participants can review and discuss the program with their physician, and if he/she does not have a physician, he/she will be referred to a source of care in the community. This brochure will be provided to the IRB for approval prior to use. The risk of phlebotomy will be minimized through the use of trained professional phlebotomists. The blood volume obtained at any phlebotomy will be no more than 20 mL. Risks related to inadvertent release of confidential information will be minimized through adherence to best practices for data collection and management. All research staff will be trained in methods for assuring participant confidentiality and safety. The information we are collecting is not of a particularly sensitive nature and we will follow exacting procedures to maintain confidentiality of the participant level data. Identifying information will be kept separate from research data and will be linked only by a participant ID, generated so as to be independent of any identifying information. The linking report and personal identifying data will be destroyed after completion of the study. No identifying information will be released in any published reports.

C. Potential Benefits and Importance of Knowledge to be Gained

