The potential direct benefits to participants include the decreased risk of developing diabetes and cardiovascular disease. In the DPP, the risk of developing diabetes was 11% per year in the “usual care” group. This risk was decreased by over 50% in the intensive lifestyle intervention group. In the HELP PD study, the group-based intervention showed significant weight loss and improvements in glucose. La Comunidad is designed to move the intervention tested in HELP PD into the Latino community, improving diabetes prevention efforts. The development of diabetes carries with it significant morbidity and mortality risk. Persons with diabetes are at an increased risk of cardiovascular diseases, in addition to increased risk of blindness, kidney failure and lower extremity amputation. The small risks of an acute cardiovascular event triggered by moderate physical activity should be far offset by the substantial potential benefit of diabetes prevention. Other potential benefits to subjects may include improved quality of life and satisfaction with self-image. Little direct benefit is expected to others; however, as persons with diabetes may impose some care-giver burden on others due to their need for frequent medical attention, it is possible that there will be some benefit related to decreased care-giver burden.

The knowledge to be gained in the proposed trial relates to our ability to implement evidence-based lifestyle interventions in different populations. As discussed above, the risks of diabetes are substantial and the potential benefits for preventing diabetes are great at the societal level; hence, the risk that participants will assume by participating in this program should be offset by the potential for public health benefit that would occur following dissemination of a successful diabetes prevention program. Furthermore, this approach could also serve as a model for other

community-based health promotion programs in the Latino community, further enhancing the potential societal benefit of the proposed project.

VI. Subject Recruitment Methods

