 participant can continue screening process.

18. Are you or any members of your household currently participating in any other medical research trials?

¹ Yes

² No

Study:

Contact study coordinator for more information before participant can continue screening process.

19. Are you planning to move from the area in the next 2 years?

¹ Yes

² No

³ Don't Know

PARTICIPANT EXCLUDED

Unable to make time commitment for length of the study

20. Are there times when you might be away for more than 2 weeks at a time that might limit participation in the intervention?

¹ Yes

² No

PARTICIPANT EXCLUDED

Travel may limit participation in intervention

21. Do you know of any reasons, health related or otherwise, that you would not be able to participate completely in a 2 year research study?

¹ Yes

² No

Reason:

Evaluate ability to participate before continuing

If eligible:

Based on these questions, you may be eligible to participate in La Comunidad. We would like to invite you to watch a brief video to learn more about the study. Are you interested in continuing the screening process?

Yes

No

If ineligible:

Based on these questions, it looks like you are not eligible to participate in La Comunidad. We really appreciate your interest in the study and hope that we can contact you in the future for other studies related to diabetes or weight loss. Would it be okay for us to keep your information on file for future studies?

Yes

No

For staff use only

Eligibility status:

Eligible

Ineligible

Refused

Pending: Explain

Call back:

MONTH

DAY

YEAR

5. Was the PAR-Q completed?

Yes

No

Check here if medical clearance is required prior to participation.

6. Measurement of HbA1c

Blood sample collected

. %

Was the HbA1c less than 5.7% or more than 6.5%?

Yes

No

PARTICIPANT EXCLUDED

HbA1c < 5.7% or >6.5%

If ineligible:

Based on the blood that we collected at the screening event, you are not eligible to participate in La Comunidad. This is because your blood sugar was *above/below* the range to qualify for the study. If you would like, please feel free to contact us in the future if you would like to be screened again. We really appreciate your interest in the study and hope that we hear from you again.

Yes

No

Date Participant is scheduled to return:

MONTH

DAY

YEAR

Time: :

AM

PM

Nature of Next Visit:

Additional Screening

Randomization

Current Status:

Eligible

Ineligible

Refused

Contact Information

Complete Legal Name

First Middle

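### The HbA1c screen-failure script gives a person above 6.5% the direction of the result and an invitation to re-screen, but neither the value nor advice to seek medical follow-up

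*Combined protocol and SAP*

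**What the plan says.** Section III.E.a (Tiered Screening Process) puts the HbA1c test last: "Those participants who have met all other eligibility criteria will then have a blood draw to determine HbA1c". It is the only glycaemic test in that sequence. Section III.D.b (Exclusion Criteria) excludes people with "Clinical history of diabetes mellitus, or newly diagnosed diabetes mellitus at screening", and attaches no notification or referral step.

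Item 6 of the screening form in Appendix B has a field for the HbA1c percentage. It then asks "Was the HbA1c less than 5.7% or more than 6.5" per cent, and a yes excludes the person. One script follows for everyone excluded at this step. It says the person is not eligible on the basis of the screening blood sample, and continues: "This is because your blood sugar was *above/below* the range to qualify for the study". The next sentence is "If you would like, please feel free to contact us in the future if you would like to be screened again". It closes with thanks.

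**The concern.** The two ways of failing this test differ in medical meaning. Below 5.7% is below the study's pre-diabetes range, and an open invitation to try again is a reasonable reply. Above 6.5% is above that range, and the protocol's own exclusion shows that it expects some people to be found with diabetes at screening. Section V.C states the stakes: "The development of diabetes carries with it significant morbidity and mortality risk".

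Read out as written, the script turns a possible diabetes signal into an eligibility message. The person learns that blood sugar was too high for the study, but not the number, and not that anyone should check it. The one action offered is to come back for another screen. Section III.H places screening in community locations rather than a clinic, and a person excluded at this point does not enter the follow-up in which Section III.H.c tracks new diabetes diagnoses.

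**Working it through.** There is no plan figure to reproduce. The check is a sentence-by-sentence reading of the script, then a comparison with every nearby text that could supply what it lacks.

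**The item 6 script**

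| Sentence | Content | Varies with direction? | Gives HbA1c value? | Mentions doctor or follow-up? |
|---|---|---|---|---|
| 1 | Not eligible, from the screening blood | No | No | No |
| 2 | Blood sugar above or below range | Yes | No | No |
| 3 | May contact the study to be screened again | No | No | No |
| 4 | Thanks | No | No | No |
| Total | | 1 of 4 | 0 of 4 | 0 of 4 |

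So a person above 6.5% and a person below 5.7% hear the same message except for one word.

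**Other texts that point to medical care**

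| Text | What triggers it | Does an HbA1c above 6.5% trigger it? |
|---|---|---|
| Diabetes Risk Test, Appendix B: talk to a doctor about further testing | A risk score of 5 or higher, before blood is drawn | No |
| Section V.B: discuss participation with a physician; referral for those without one | Being a potential participant, before enrolling | No |
| PAR-Q (Section V.B and Appendix B): medical clearance | A positive answer on readiness for physical activity | No |
| Section III.D.b: exclusion of newly diagnosed diabetes | Diagnosis at screening | Exclusion only; no notification or referral |

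The second row comes closest. It promises that "if he/she does not have a physician, he/she will be referred to a source of care in the community". Its purpose, though, is to let people discuss taking part, and someone just excluded has no participation left to discuss.

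**What an above-range result means here.** The protocol does not define a single reading as a diagnosis, and the Diabetes Risk Test says that only a doctor can settle the question. The result is therefore a signal that needs checking, which is the message the script omits.

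**Size.** The number of people affected would be the number of HbA1c screens multiplied by the share above 6.5%. Neither is in the documents, so no figure or range is given.

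**The case against.** The strongest objection is that absence cannot be shown from this text. The screening form is damaged: it begins at item 5, and a Yes/No pair after the script has no visible question, so at least one line nearby is lost. The usual places for a result-notification step are also unavailable: the consent pages were removed, the Manual of Procedures (Section III.I) is not supplied, and the screening flow figure is not shown. Section VII puts consent before any blood draw, so the consent form may well cover the point. All of this stands. It limits the conclusion to the visible wording, and it would be wrong to say that the trial has no referral process.

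A second objection is that people are not left without a route to care. Section V.B covers all potential participants, not only those enrolled, and the risk test has already sent higher-scoring people to a doctor. This stands in part: the general advice exists, but none of it tells anyone what their HbA1c showed or responds to that result.

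Third, the script refers back to blood collected at the screening event, so it is probably a later contact made once the result is known. That is a fair reading. It adds weight to the wording, since this may be the conversation in which the person learns the result.

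Finally, the study questionnaire lists having no usual source of care as one possible answer. That shows only that the study allows for the situation. It says nothing about how common it is among people excluded on HbA1c.

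**Conclusion.** The point holds as a minor participant-safety matter, with medium confidence. In the visible text, a person screened out with an HbA1c above 6.5% is told the direction of the result and invited back. They are not given the value or advised to have it checked, and no other visible text fills the gap for that result. The consequence cannot be quantified.

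The conclusion assumes that the script is used as printed and that no line carrying this advice was lost in extraction. It would fall away if the consent form or the Manual of Procedures already provides for notifying people of a high HbA1c. Nothing here affects the 5.7–6.5% eligibility range, the primary analysis or the sample size.

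**What to change.** Leave the below-range wording as it is. For people above range, keep the re-screening invitation and add two things: the HbA1c value in writing, and a sentence advising follow-up with their physician or, if they have none, offering the community referral already described in Section V.B. Suitable wording would be: *Your HbA1c was [value]%. This may be a sign of diabetes. Please have it checked by your doctor; if you do not have one, we can refer you to a source of care.*

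Add a referral check box to item 6, on the model of the medical-clearance box at item 5. Align the text with any result-notification wording in the consent form or Manual of Procedures; if either already covers this, a cross-reference on item 6 is enough.

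The cost is a short script addition, one check box and an IRB submission of the revised participant-facing text. The referral route is one the protocol already describes.
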